10.2. Lesion Percent (%) Reduction at EOS

At the EOS visit, the number of lesions will be reported. The percent change in number of lesions will be calculated as described in Section 10.3. Based on the percent reduction of lesions at EOS, subjects will be assessed and assigned to one of 2 categories: $\geq 90\%$ reduction of lesions, $<90\%$ reduction in lesions. Subject counts and percentage of subject for each of these categories will be displayed by treatment group over the entire study and by visit.

10.3. Change and Percent Change in Number of Lesions

Number of lesions present will be recorded at each treatment visit as well as EOS. For each post baseline treatment visit, the change in number of lesions from baseline will be calculated. Summary statistics of number of lesions will be displayed for each treatment visit by treatment group. Summary statistics of change in number of lesions from baseline will also be displayed.

Percent change of lesions will be calculated at each post baseline visit. Percent change will be calculated using the following formula (in formula below, lesions refers to treatable lesions):

$$\text{Percent (\%)} \text{ Change} = \left(\frac{\text{Lesions at Post Baseline Visit} - \text{Lesions at Baseline Visit}}{\text{Lesions at Baseline Visit}} \right) * 100$$

Analysis of percent change in number of lesions will be carried in the same manner as change in number of lesions.

10.4. Children's Dermatology Life Quality Index (CDLQI)

At each study visit, the CDLQI will be administered with specific instruction to focus on the impact of molluscum and not any other possible concomitant skin ailments. The CDLQI is a 10-item questionnaire completed by subject/parent to assess skin condition over the past week. From responses to that questionnaire, a composite score is calculated. The calculated composite score is the sum of the individual 10 items of the CDLQI and can range from 0-30. For each item on the CDLQI, a score of 0-3 is assigned using the following scores per response:

- Not at all= 0
- Only a little= 1
- Quite a lot= 2
- Very much (or Prevented School, Question 7 only)= 3

Larger composite CDLQI scores indicate skin condition is having more effect on subjects' lives. If one question is left unanswered, it is scored 0 for the total composite score. If two or more questions are left unanswered, the questionnaire is not scored and will be counted as missing. Question 7 has 2 parts: one applicable if the subject is in school; the other if the subject is on vacation (holiday). Subjects are supposed to only respond to 1 of these questions. Should the subject respond to both questions, the higher of the 2 scores will be counted.

The composite score from the CDLQI will be treated as a continuous variable. Descriptive statistics of the composite score will be displayed by visit and EOS for each treatment group considering all subjects. The CDLQI has only been validated for subjects between 4-16 years old age. As a result, analyses will only consider subjects 4-16 years old.

Descriptive statistics for each of the individual items (questions) in the CDLQI will be generated by visit. The CDLQI has a series of domains, each with its own score. The domain scores are calculated based on responses to specific question(s) within the CDLQI. Descriptive statistics of each domain score will be provided by visit. Those domains along with the questions used to derive and the maximum score for each domain are include in Table 1 below:

Table 1

Domain	CDLQI Question(s)	Maximum Domain Score
Symptoms and Feelings	1,2	6
Leisure	4,5,6	9
School or Holidays	7	3
Personal Relationship	3,8	6
Sleep	9	3
Treatment	10	3

In addition, a sensitivity analysis of the composite CDLQI score will be performed to support the findings of the analyses described above. For the sensitivity analysis, the same methods described above with the only exception that all subjects enrolled in the study will be included in the analysis. That means subjects below 4 years of age as well as subject greater than 16 years of age will be considered. This analysis will be included so that summaries will be available that include all subjects enrolled in the study.

10.5. Subject Reported Spread of Molluscum Lesions

Sibling information will be collected for subjects enrolled in the study. Subjects who have at least one sibling who does not exhibit molluscum lesions at baseline will be considered for this analysis. For those subjects, the count and percent of subjects who had a sibling who was clear at baseline but showed lesions post baseline will be

summarized by treatment group. Note: subjects who do not have a sibling free of molluscum lesions at baseline will not be considered for this analysis.

11. Safety Analysis

All safety analysis will be based on the Safety Population. Analysis using the Safety population will be based on the treatment received.

11.1. Extent of Exposure

The total number of lesions treated will be collected by visit over the duration of the study. For each visit, the number of lesions treated will be determined by subtracting the reported number of lesions not treated from the total number of lesions reported.

Summary statistics of number of lesions treated at visits Day 1, Day 21, Day 42 and Day 63 will be generated by treatment group. In addition, the total number of treatment visits and total number of lesions treated will be displayed.

11.2. Adverse Events

Adverse events summaries will only consider Treatment Emergent Adverse Events (TEAEs). TEAEs are defined as those adverse events that occurred after dosing and those existing adverse events that worsened during the study. If it cannot be determined whether the adverse event is treatment emergent due to an incomplete (partial) onset date, the adverse event will be considered to be treatment emergent. Verbatim terms entered into the clinical database via the EDC system will be mapped to preferred terms and system organ classes using the most current version of Medical Dictionary for Regulatory Activities (MedDRA) available.

Each adverse event summary will be displayed by treatment group. Summaries that are displayed by system organ class and preferred terms will be ordered by descending order of incidence of system organ class and preferred term within each system organ class. Summaries of the following types will be presented:

- Overall summary of the TEAEs which contain an overview of each item below.
- Subject count and incidence rate of TEAEs by MedDRA system organ class and preferred term.
- Subject count and incidence rate of TEAEs by MedDRA system organ class, preferred term and highest severity. At each level of subject summarization, a subject is classified according to the highest severity if the subject reported one or more events.
- Subject count and incidence rate of TEAEs by MedDRA system organ class, preferred term and closest relationship to study drug (Related/Not Related). Related AEs are those reported as “Definitely”, “Probable” or “Possibly”. At each level of subject summarization, a subject is classified according to the

closest relationship if the subject reported one or more events. Adverse events with missing relationship will be considered related for this summary.

- Subject count and incidence rate of Serious TEAEs by MedDRA system organ class and preferred term.
- Subject count and incidence rate of TEAEs leading to study discontinuation by MedDRA system organ class and preferred term.

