- a. Screening can occur up to 14 days prior to Study drug application on Day 1. Screening can occur on the same day as treatment Day 1/Study drug application. An IRB-approved ICF must be signed before any study specific procedures are performed.
- b. Subjects may be scheduled 21+/- 4 days after treatment in the event of scheduling conflict. If possible the next treatment or study visit should be scheduled 21 days from the day of the subject's last study visit. The 24 hour follow-up may be conducted at +/- 3 hours. Study medication should be removed after the 24 hour draw is completed.
- c. At end of the study (EOS, ~Day 84), all subjects with unresolved molluscum lesions or unresolved treatment-emergent AEs, will be treated by the investigator per local standard of care. Patients who clear all lesions at study visits prior to ~Day 84 will complete all study related assessments that were required at the EOS visit and will not need to return for further assessment. A study completion form will be completed on the day they are cleared.
- d. Confirmation of eligibility criteria.
- e. Demographics: date of birth, sex, race/ethnicity will be collected.
- f. Vital signs (e.g., temperature & heart rate) will be obtained at screening and at each treatment prior to application of Study drug.
- g. Limited physical examination. Symptom- or AE-directed physical examination may be performed if warranted. (See Source/CRF for further outline of assessment.)
- h. Regional lesion counts (head/neck, trunk, upper/lower extremities) should be performed.
- i. LSR assessment will be performed by the Investigator or trained personnel with a protocol-specific LSR form at each treatment visit and the EOS visit.
- j. CDLQI assessment to be completed prior to Study drug application and at EOS visit. CDLQI must be repeated if the first treatment is not completed within 7 days.
- k. To be performed prior to Study drug application and at EOS in any females of childbearing potential (females that are capable of menstruating).

- l. Photography of molluscum lesions will occur at selected clinical sites only.
- m. Study drug may be gently removed from individual lesions prior to 16 hours of application in the event of significant blistering, significant pain or treatment emergent AEs. Study drug should not be removed from the remaining unproblematic lesions until the 24 hour time point is reached. Every effort should be made to complete the PERIT at 24 hours after application.

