Adverse event means any untoward medical occurrence associated with the use of a drug in humans, whether or not considered drug related.

An AE can be any unfavorable and unintended sign, symptom, or disease (new or exacerbated) temporally associated with the use of the investigational product, regardless of whether it is considered to be related to the investigational product.

The following are examples of AEs:

- Exacerbation of a chronic or intermittent preexisting condition, including an increase in frequency or intensity of the condition
- New conditions detected or diagnosed after investigational product administration, even if they were present before the start of the study
- Signs, symptoms, or the clinical sequelae of a suspected interaction with another medical product

Examples of AEs do not include the following:

- Medical procedures (The medical condition that led to the procedure as the AE should be reported.)
- Situations that are unwanted by the subject but in which an untoward medical occurrence did not occur, for example social inconvenience after admission to a hospital
- Anticipated day-to-day fluctuations of a preexisting disease or condition (present or detected before enrollment) that does not worsen overall

- Expected progression of the disease being studied, including signs or symptoms of the disease, unless progression is more severe than expected for the subject's condition

AEs may include pretreatment or post treatment events that occur as a result of protocol-mandated procedures (e.g., invasive procedures, modification of the subject's previous therapeutic regimen). AEs should be captured even if they occur during periods without drug treatment or post treatment periods. AE collection begins once the patient has signed informed consent and will continue until the EOS visit has been completed.

The investigator is responsible for performing periodic and special assessments for AEs. The investigator and study personnel will note all AEs mentioned by the subject starting from the day the informed consent is signed and during administration of the investigational product, until the end of study visit (Day 84). All clinical complaints volunteered by or elicited from the subject or parent/guardian during the study will be recorded on the appropriate page of the eCRF for the study period indicated. The subject and parent/guardian will receive appropriate treatment and medical supervision for any AE that occurs.

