5.4 ASSESSMENT OF INTENSITY

The investigator will assess the intensity for each AE and SAE reported during the study. The assessment will be based on the investigator's clinical judgment.

The classifications in [Table 1](#) should be used in assigning intensity of each AE recorded in the eCRF.

Table 1. Classification of AEs by Intensity^a

Intensity	Definition
Mild AE (Grade 1)	An event that is easily tolerated by the subject, causing minimal discomfort and not interfering with everyday activities
Moderate AE (Grade 2)	An event that is sufficiently discomforting to the extent of interfering with normal everyday activities
Severe AE (Grade 3)	An event that prevents the subject from performing normal everyday activities
Life-threatening or disabling AE (Grade 4)	An event that, at the time of occurrence, put the subject at risk of death or resulted in a persistent or significant disability or incapacity
Death related to AE (Grade 5)	An event that resulted in death

AE: adverse event.

a From Common Terminology Criteria for Adverse Events (CTCAE), Version 4.0.

Any AE that changes in intensity or grade during its course will be recorded in the eCRF at the highest level experienced by the subject.

An AE that is assessed as severe should not be confused with an SAE. Severity is a category used for rating the intensity of an AE (such as mild, moderate, or severe myocardial infarction). However, the event itself may be of relatively minor medical significance, such as a severe headache. Both AEs and SAEs can be assessed as severe. An AE is considered serious when it meets one of the predefined outcomes described in [Section 5.2](#).

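### The worsening part of the TEAE rule is not tied to first application and cannot be derived from a record that keeps only the highest grade, so an AE ongoing at first dose that changes grade can be misclassified

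*SAP*

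**What the plan says.** SAP 11.2 defines treatment emergence in one sentence: "TEAEs are defined as those adverse events that occurred after dosing and those existing adverse events that worsened during the study". All AE summary tables are restricted to TEAEs: incidence, highest severity, relationship, serious events and events leading to discontinuation. The one tie-break concerns onset: "If it cannot be determined whether the adverse event is treatment emergent due to an incomplete (partial) onset date, the adverse event will be considered" treatment emergent. Nothing is said about an unknown date of worsening.

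Protocol 5.1 sets the collection period: "AE collection begins once the patient has signed informed consent and will continue until the EOS visit has been completed". The footnotes to the schedule of assessments set the gap between consent and dosing: "Screening can occur up to 14 days prior to Study drug application on Day 1", with same-day screening also allowed.

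Protocol 5.4 says how a change in grade is stored: "Any AE that changes in intensity or grade during its course will be recorded in the eCRF at the highest level experienced by the subject". Neither document asks for the grade at first application, the date of a grade change, or a new record when an AE worsens. The eCRF itself is not among the documents.

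**The concern.** The second part of the definition exists to catch an event that was present before treatment and became worse on it. Applying it takes two facts: that the grade rose, and that it rose after the first application. The recording rule in Protocol 5.4 keeps neither. Once the highest grade replaces the earlier one, an AE that peaked before dosing and an AE that worsened under treatment leave the same record.

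The wording adds a second uncertainty. Worsening is placed within the study, not after first application. A programmer who takes the study to begin at consent would count a rise in grade that happened before any drug was given.

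Safety is a secondary objective, and an AE classed as not treatment emergent leaves every AE summary in SAP 11.2. No programming step at the analysis stage can restore a pre-dose grade that was never kept.

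**Working it through.** The plan gives no figure to reproduce: there is no power calculation and no expected AE rate. The check has three parts.

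**1. Two histories, one record.** Both AEs start on Day -5 as mild and are ongoing at Day 1.

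| | Day -5 | Just before first application | Peak after first application | Stored under Protocol 5.4 |
|---|---|---|---|---|
| A | mild | mild | moderate | onset Day -5, moderate |
| B | mild | moderate | mild | onset Day -5, moderate |

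A worsened after dosing and B did not. The onset date and highest grade are identical, so no rule using those two fields can classify both correctly. Both onset dates are complete, so the partial-date tie-break does not apply.

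**2. All grade patterns for an AE ongoing at first application.** Let o be the grade at onset, d the grade just before first application and p the peak grade afterwards, each from 1 to 3. That gives 3 × 3 × 3 = 27 patterns. True worsening was defined in two ways, both of which are reviewer's assumptions: p above the worst pre-dose grade, p > max(o, d), which holds in 5 patterns; and p above the last pre-dose grade, p > d, which holds in 9 (3 values of o × 3 pairs with p > d).

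| How the SAP rule might be programmed | Patterns counted as TEAE | False / missed, worst pre-dose grade as reference | False / missed, last pre-dose grade as reference |
|---|---|---|---|
| Onset date decides | 0 | 0 / 5 | 0 / 9 |
| Any rise above onset grade since consent, full history known | 13 | 8 / 0 | 8 / 4 |
| Every AE ongoing at dose counts | 27 | 22 / 0 | 18 / 0 |

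From the stored record alone, a highest grade of 1 always means no worsening (1 pattern). A highest grade of 2 (7 patterns) or 3 (19 patterns) is compatible with both answers under either reference. If the chosen pre-dose reference grade and the post-application peak were both on file and the rule used them, all 27 patterns would be classified correctly. These are counts of logical patterns, not expected frequencies.

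**3. Size.**
- Largest share of collection time before dosing, with 14 days of screening and 84 days on study: 14 / (14 + 84) = 14.3%. With same-day screening it is 0%.
- Effect of one misclassified subject on an incidence: 1/16 = 6.25 points (one group at its planned size), 1/32 = 3.1 points (16 + 16), 1/40 = 2.5 points (maximum enrolment).

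The number of affected AEs would need an AE rate, a typical screening length and the fraction that change grade. The documents give none of these, so no estimate is offered.

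**The case against.** The case that this is only a wording matter has several sound parts.

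- *During the study can mean from Day 1.* SAP section 3 measures study duration from Day 1 and calls screening pre-study, and SAP section 6 treats a subject as enrolled only after a first treatment. A reader might infer from SAP 11.2 that a rise in grade before dosing is definitely counted as treatment emergent. The documents do not support that; they leave it open. An explicit anchor would still remove the doubt, and this reading does nothing for the missing grade history.
- *Exacerbations are AEs in their own right.* Protocol 5.1 lists "Exacerbation of a chronic or intermittent preexisting condition, including an increase in frequency or intensity of the condition" as an AE, so such an event can carry its own post-dose onset date. This takes most worsening of pre-existing conditions out of the problem. It does not cover an AE that began after consent and is already on file.
- *Skin reactions are captured elsewhere.* Protocol 4.2.2 lists an LSR assessment ahead of application on Day 1. SAP 11.3 adds a separate LSR form at 1, 7 and 14 days after each treatment, and SAP 11.4 tabulates PERIT at 24 hours. No TEAE filter is stated for either. It would be wrong to infer that a skin event dropped from the TEAE tables survives only in a listing.
- *The eCRF is unseen.* Protocol 5.4 says which grade is kept. It does not say that there is one line per AE, and it does not rule out a severity-change field. The fix is conditional for this reason.
- *Few pre-dose AE records are likely.* The screening list in Protocol 4.2.1 names no AE review, and Protocol 4.2.2 takes changes since screening as medical history. Protocol 5.1 nevertheless has investigators noting AEs from the day of consent.
- *The consequence is modest.* The trial is open-label and descriptive, without a control arm, and all data are listed by subject.

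These points narrow the scope. They do not resolve the conflict between a rule that depends on worsening and a record that keeps only the peak.

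**Conclusion.** The point holds in a limited form. As written, the worsening part of SAP 11.2 cannot be derived from the record that Protocol 5.4 specifies, and it lacks a first-application anchor. The AEs at risk start between consent and first application, are still ongoing at that application, and change grade. They can be misclassified, and the direction depends on how the rule is programmed.

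A reader might infer that AEs starting in screening are misclassified as a class. They are not. AEs that resolve before dosing can be excluded on dates, assuming a stop date is recorded. AEs that keep one grade are handled correctly by both the onset-date and the any-rise reading. A highest grade of 1 leaves no room for worsening.

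The effect is probably confined to very few events, each worth 2.5 to 6.25 percentage points of subject incidence. This rests on the eCRF holding no more than Protocol 5.4 describes. It is worth settling because the lost information cannot be rebuilt at analysis and the remedy is cheap.

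**What to change.** 1. **SAP 11.2, definition.** Define a TEAE as an AE with onset at or after the first application of study drug, or an AE with earlier onset whose severity rises after the first application above its last pre-application grade.
2. **SAP 11.2, default.** Extend the treat-as-emergent default to an AE that is known to have worsened but whose date of worsening is unknown. Limit it to a known rise, so that AEs with a steady grade are not swept in.
3. **Protocol 5.4 and the CRF completion instructions.** Keep the highest-grade rule, except where an AE present at first application worsens afterwards. Record that worsening as a new line with its own onset date and grade. If the eCRF already captures grade changes with dates, say so in the SAP and leave the CRF as it is.
4. **Data already collected.** Before database lock, query the grade at first application and the date of any worsening for the AEs recorded with pre-dose onset.

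The cost is one revised sentence and one added default in the SAP, one CRF instruction and a handful of queries. The downside is that a few events appear as two lines in the listings. Subject incidence is not inflated, because SAP 11.2 counts subjects and the pre-application line is not itself treatment emergent.

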11.3. Targeted Adverse Events- Local Skin Reactions

Local skin reactions (LSRs) to treatment reported by investigators and subjects will be recorded as adverse events. LSRs will include the following adverse events: blistering, pain, pruritus, erythema, edema, erosion/ulcerations, flaking/scaling/dryness, scabbing/crusting and pigmentation changes. LSRs will be identified via a medical review of adverse events reported. LSRs will be coded and summarized using similar methods as described in Section 11.2 for adverse events.

Summaries of LSRs will include the following:

- Subject count and incidence rate of LSRs by MedDRA system organ class and preferred term.
- Subject count and incidence rate of LSRs by MedDRA system organ class, preferred term and highest severity. At each level of subject summarization, a subject is classified according to the highest severity if the subject reported one or more events.
- Subject count and incidence rate of LSRs by MedDRA system organ class, preferred term and closest relationship to study drug (Related/Not Related). Related LSRs are those reported as “Definitely”, “Probable” or “Possibly”. At each level of subject summarization, a subject is classified according to the closest relationship if the subject reported one or more events. LSRs with missing relationship will be considered related for this summary.
- Subject count and incidence rate of serious LSRs by MedDRA system organ class and preferred term.
- Subject count and incidence rate of LSRs by LSR types described in the first paragraph of this section.

In addition, information from a study specific from of assessment of local skin reactions (LSRs) will be collected 1, 7 and 14 days after each treatment and at the EOS visit. The following clinical responses will be recorded: blistering, erythema, edema, erosion/ulcerations, flaking/scaling/dryness, scabbing/crusting and pigmentation changes (hyperpigmentation or hypopigmentation) and scaring. Possible graded responses for each of these LSRs are: None, Mild, Moderate, Severe. Only the most severe reaction grade will be recorded at each assessment. This grading of LSRs is on a distinct scale

based on the descriptions in the LSR guide and severity of these reactions are not the same as the adverse analyses described in Section 11.2. Overall counts and percentages for each of the reactions will be displayed by treatment group. Summaries of each reaction by highest severity and last observed assessment will be shown.

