2.2.1 Inclusion Criteria

To qualify for inclusion in this study, subjects must:

1. Be healthy subjects, ages 2 years and older.
2. Patients with 1-20 lesions may be enrolled and treated in the ‘standard treatment’ group but are not eligible for the exposure study OR

Patients with 21 or more lesions may only be enrolled in the ‘exposure group’. Subjects participating in the Exposure group must have at least 21 lesions treated at Day 1 to qualify.

3. Be otherwise medically healthy with no clinically significant medical history as determined by the investigator. *Patients exhibiting active Atopic Dermatitis may be enrolled.*
4. Refrain from application of all topical agents including alcohol-based sanitary products and sunscreens for a minimum of 4 hours before Study drug application. Topical agents including alcohol-based sanitary products and sunscreens may be used after application of the study drug so long as they are not applied to or near treated skin.
5. Refrain from swimming, bathing or prolonged immersion in water until the Study drug is removed.
6. Have the ability or have a guardian able to follow study instructions and be likely to complete all study requirements.
7. Provide assent in a manner approved by the institutional review board (IRB) and have a parent/guardian provide written informed consent as evidenced by signature on IRB approved assent/consent forms.
8. Provide written authorization for use and disclosure of protected health information.
9. Agree to allow photographs of all selected lesions to be taken and/or send photos via text or email to the study team for assessment at 24 hours’ post treatment. These images may be used on handouts in future trials, for training purposes, as part of the study data and/or marketing package. *Photographs will be de-identified to those outside the research team. Effort will be made to ensure that no photos with identifiable features are obtained.*

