2.2.2. Secondary Objectives

The secondary objectives of this study are:

- to assess the safety of VP-102, when applied once every 21 days for up to 4 applications, to treated molluscum lesions on subjects 2 years old and older by assessing adverse events including expected local skin reactions, physical examinations and concomitant medications throughout the study compared to baseline.
- To assess the efficacy of VP-102 in the treatment of molluscum lesions as assessed by clearance or reduction of treated molluscum lesions as compared to baseline.

- To assess the impact of VP-102 treatment on quality of life of subjects as assessed via the administration of the Children's Dermatology Life Quality Index (CDLQI).

3. Study Design

This is a Phase 2 study that will be conducted in the United States to determine the systemic exposure, efficacy, safety and impact on quality of life of VP-102 (0.7% cantharidin) following treatment of molluscum lesions for up to 4 treatments, 21 days apart, with VP-102 in up to 40 subjects (2 years or older). Subjects to be included in the Exposure group must have at least 21 lesions treated at Day 1 to qualify. The Standard treatment group will consist of subjects with fewer than 21 lesions treated at Day 1. Duration of molluscum lesions prior to Day 1 will be recorded but will not be an inclusion/exclusion requirement.

Study drug, VP-102, will be supplied in single-use applicators, with one applicator sufficient to treat at least 50 molluscum lesions. If required due to the number and size of lesions, a second single-use applicator may be used. No more than 2 applicators will be permitted per subject per treatment. In the Exposure group, blood samples for systemic exposure evaluation will be collected on Day 1, prior to the Study drug application (T=0), and 2 (\pm 30 minutes), 6 (\pm 1 hour) and 24 (\pm 3 hours) hours post-application. The film-forming Study drug solution will be applied and left on the lesions for approximately 24 hours before the subject and/or parent/guardian washes the dried film off the lesions with soap and warm water. For those subjects in the Exposure group, the dried film will be removed after the 24-hour blood draw is obtained. Study drug treatment may be removed prior to the 24-hour time point in the event significant blistering, uncontrollable pain or treatment emergent AEs are experienced.

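### The LSR-form tables in SAP 11.3 have no baseline reference, so skin signs already present on Day 1 may be tabulated as local reactions to VP-102

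*SAP*

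**What the plan says.** SAP 2.2.2 sets the safety objective as an assessment of adverse events "including expected local skin reactions, physical examinations and concomitant medications throughout the study compared to baseline". Protocol 1.6 also frames safety, including LSRs, as a comparison with baseline.

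SAP 11.3 handles LSRs in two ways. LSRs recorded as adverse events are summarised by methods similar to SAP 11.2. Separately, a study-specific form grades each sign: "Possible graded responses for each of these LSRs are: None, Mild, Moderate, Severe". For the form, "Overall counts and percentages for each of the reactions will be displayed by treatment group", and "Summaries of each reaction by highest severity and last observed assessment will be shown". Section 11.3 names no baseline grade, shift table or new-or-worsened condition for these data.

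The form's timing differs between the documents. SAP 11.3 says the form data "will be collected 1, 7 and 14 days after each treatment and at the EOS visit". Footnote i to the protocol's Schedule of Assessments says "LSR assessment will be performed by the Investigator or trained personnel with a protocol-specific LSR form at each treatment visit and the EOS visit". SAP section 3 follows the protocol on this.

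On entry, Protocol 2.2.1 item 3 states: "Patients exhibiting active Atopic Dermatitis may be enrolled". Protocol 2.2.2 item 5 excludes earlier molluscum treatment, including cantharidin, curettage and freezing, only within the past 14 days.

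**The concern.** The objective asks for a comparison that the planned form tables do not make. Several of the graded signs (erythema, scaling or dryness, crusting, pigment change, scarring) can exist before any VP-102 is applied. A sign that persists to a later assessment would appear in the counts, in the highest grade and possibly in the last grade, and would look the same as a reaction to the drug.

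Both groups receive VP-102 and differ by lesion count, so no untreated arm shows the background level. For the form data, the subject's own pre-application grade is the natural reference. Scarring is the most exposed sign. It is on the form but not in the list of LSR adverse events in SAP 11.3, so the form table is its only planned LSR summary. A scar reported as an ordinary adverse event would still reach the SAP 11.2 tables.

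**Working it through.** The plan states no expected LSR rate, so there is no figure to reproduce. The check is mainly textual.

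**1. Is a baseline scheduled?** Yes, in the protocol. Section 4.2.2 lists the LSR assessment as item 8 and drug application as item 11, and the synopsis uses the same order. Protocol 2.1 and 2.3.1 make the Skin Quality Assessment (pigment change and scarring) part of the LSR assessment.

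**2. Does another SAP rule supply the comparison?**
- SAP 11.2 counts an existing event only if it worsened. This applies to LSRs handled as adverse events. SAP 11.3 says that the form's severities are not those of the adverse event analyses, so the rule does not carry over.
- SAP 9.2 defines baseline, but within the efficacy section, and 11.3 does not invoke it.
- SAP 11.5 specifies change from baseline for temperature and pulse. Nothing similar is written for the form.

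**3. Can these signs be present at entry?** Yes. Atopic dermatitis may be active, and SAP 9.7 lists it as a possible subgroup. Treatment more than 14 days earlier is allowed. One retrospective cantharidin series in Protocol 1.2.2 reports erythema lasting up to 3 weeks (21 days), which is longer than the 14-day window, and pigment change in 8%.

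**4. Does the answer depend on whether Day 1 enters the highest grade?** No. If it did, a purely pre-drug grade could be the reported maximum. If it does not, a Day 1 sign that persists to a post-application assessment is still counted.

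**5. Illustration of size (assumption, not an estimate).** For a single sign, let p0 be the share of subjects with a persisting pre-application finding, and q the rate of new onset in the rest. For q, take 8% (pigment change) and 37% (erythema) from the same series. The range for p0 is assumed.

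- Tabulated rate = p0 + (1 − p0)q
- New-onset rate = (1 − p0)q
- Pre-existing share of tabulated cases = p0 / tabulated rate

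| p0 | Pigment: tabulated / new / share pre-existing | Erythema: tabulated / new / share pre-existing |
|---|---|---|
| 5% | 12.6% / 7.6% / 40% | 40.15% / 35.15% / 12% |
| 10% | 17.2% / 7.2% / 58% | 43.3% / 33.3% / 23% |
| 20% | 26.4% / 6.4% / 76% | 49.6% / 29.6% / 40% |
| 40% | 44.8% / 4.8% / 89% | 62.2% / 22.2% / 64% |

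Worked row for pigment at p0 = 10%: 0.10 + 0.90 × 0.08 = 0.172; new 0.90 × 0.08 = 0.072; 0.10 / 0.172 = 0.58. With 32 subjects (16 + 16), that is 5.5 tabulated and 2.3 new.

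The chance that at least one of 32 subjects has such a finding is 1 − (1 − p0)^32: 81% at p0 = 5% and 97% at p0 = 10%. One subject is 1/32 = 3.1 points overall and 1/16 = 6.25 points in a group of 16. With the full 40 enrolled, one subject is 1/40 = 2.5 points.

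The model leaves out worsening of an existing sign. A subject whose sign worsens is a genuine case, so the new-onset column understates true reactions, most of all for erythema.

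**The case against.** The other side has real force on several points.

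- **A baseline rule already exists for LSRs.** Those recorded as adverse events are summarised by methods similar to the treatment-emergent analysis and are split by relationship to drug. This stands. A reader might infer that the Day 1 grade is the only means of separating drug effect from existing disease; for LSRs as a whole that is wrong. The gap is confined to the form tables, and to scarring as an LSR.
- **Pooling of Day 1 is not shown.** A reader might infer that the Day 1 form feeds the highest-severity summary. Every form time listed in SAP 11.3 is after application, so the documents do not support that. They do conflict on when the form is completed.
- **Miscounting is not certain.** A reader might infer that existing signs will be reported as reactions. Grading follows an LSR guide that is not in the documents and may tell raters to record only treatment-related change. The supportable word is *may*.
- **Frequency and duration are unsourced.** Nothing says that many children carry these signs, or that scarring and pigment change last through 12 weeks. One series in Protocol 1.2.2 describes hypopigmentation as temporary. Nor can one rate of having any sign be read into tables built sign by sign.
- **A worsened-only count could hide reactions.** Only the most severe grade is recorded at each assessment. A child with moderate eczema redness on Day 1 and a new moderate reaction elsewhere would show no change. This stands and limits the remedy.
- **The consequence is limited.** The likely bias overstates harm, the study is descriptive, and by-subject listings would show any Day 1 grades collected. This is true, but listings do not correct a table, and the objective is still a comparison with baseline.

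**Conclusion.** The point stands for the LSR-form summaries. They lack the baseline reference that the safety objective calls for, although the protocol schedules an assessment that could supply it. Signs present at entry may therefore be tabulated as local reactions to VP-102.

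The size cannot be determined. The illustrative figures depend entirely on the assumed p0, on new-onset rates borrowed from one retrospective series, and on leaving out worsening. The conclusion also assumes that raters grade what they see rather than only treatment-related change, and the documents do not settle that. This is an inexpensive improvement to a descriptive safety analysis; it does not undermine the primary exposure question.

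**What to change.** In SAP 11.3:

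1. Reconcile the form schedule there (1, 7 and 14 days after each treatment, and EOS) with the treatment-visit schedule in the protocol and SAP section 3. Confirm that the Day 1 assessment uses the same four-level scale.
2. Define the Day 1 pre-application grade as the LSR baseline and state that it does not enter the highest-severity summary.
3. Add a shift table of Day 1 grade by highest and by last post-application grade, for each sign that the Day 1 assessment covers. The protocol's LSR list has erythema (with swelling), scaling, dryness, crusting, pigment change and scarring. The SAP form adds blistering and erosion/ulceration and grades edema separately, so these may have no matching Day 1 grade.
4. Keep the planned raw counts beside the shift table. Do not replace them with a worsened-only count.

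The cost is one added table and the work of reconciling the schedule. If the Day 1 form is on the same scale, no new data are needed. If it is not, the SAP should say for which signs the comparison cannot be made.
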